#### **Rationale of Study**

#### Asthma and FeNO

Asthma is a disease with marked heterogeneity in its clinical course and in its response to treatment. Variability in the type of airway inflammation may underlie this heterogeneity. Despite treatment with inhaled glucocorticoids, many patients continue to have uncontrolled asthma that requires more intensive therapy. Based on the ethnobotanical uses of Tiger Milk mushroom in treating asthma, its significant anti-inflammatory activity and also the positive feedbacks received from asthmatic volunteers using LiGNO™ Tiger Milk Mushroom, it is worthwhile to explore the potential of Tiger Milk Mushroom to be used as an immunomodulatory treatment to support conventional therapy through a proper designed clinical study. This will allow patients with uncontrolled asthma to obtain access to a new complementary therapy which they may benefit from. The objective of the study is to investigate the efficacy of L. rhinocerus to be used as a complementary therapy in improving symptoms, preventing exacerbations and reducing underlying airway inflammation in asthma patients.

 $FE_{NO}$  (fractional exhaled nitric oxide) is the only available point of care test to assess type-2 inflammation in asthma. Raised  $FE_{NO}$  with blood eosinophilia should be regarded as treatable traits of type 2 inflammation.  $FE_{NO}$  maybe useful for providing

feedback to both physicians and patients taking asthma therapy (in particular inhaled corticosteroids, ICS) particularly when the spirometry is normal.

 $FE_{NO}$  values can be influenced by several non-disease-related factors, thus filling in a questionnaire for NO measurement is recommended. Confounding factors could be related to the patient, like genetics, sex, weight and height, diet (*i.e.*, coffee) or taking drugs such as anti-inflammatory medications; also current smoking and atopy seem to influence  $FE_{NO}$  levels. Allergen exposure is associated with higher levels of  $FE_{NO}$  but they could decrease during the early phase of allergic response. Smoking is an important determinant of  $FE_{NO}$  levels and current smokers exhibit lower levels of  $FE_{NO}$  in comparison to ex-smokers and never smokers. Both active and passive smoking have effects on lowering  $FE_{NO}$  as demonstrated in healthy adults and in both adults and children suffering from asthma, regardless their allergy status.

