 $FE_{NO}$  could be influenced also by viral respiratory infections. Age seems to be important too, especially in children, but correlation between age and sex has still to be defined. Recently, also ethnicity seems to have a role in  $FE_{NO}$  results, impacting clinical management.

Moreover, there are also technical confounding factors in  $FE_{NO}$  measurement, like the NO analyzer used, measurement technique, exhalation flow rate or nasal NO contamination. Spirometry could also influence  $FE_{NO}$  results, thus it should not be performed first.  $FE_{NO}$  could increase due to bronchodilation and it could decrease due to bronchoconstriction.

Reference values have been described for  $FE_{NO}$ . In clinical practice,  $FE_{NO}$  <25 ppb in adults is considered the normal value.  $FE_{NO}$  levels between 25-50 ppb in adults (20-35 ppb in children) should be contextualized within the clinical context.

The eosinophilic asthma phenotype is characterized by sputum eosinophils  $\geq$ 3% and identifies patients with a good response to corticosteroids and T2 immunomodulators. FENO values >50 ppb are likely connected with airway eosinophilic inflammation and this data may be used to predict a response to anti-inflammatory therapy, while low FENO <25 ppb correlates with less eosinophilic inflammation and responsiveness to corticosteroids. Diagnostic FENO cut point in well controlled asthma is usually indicated by normal values. FENO >30 ppb is usually associated with uncontrolled asthma.

According to GINA guidelines, following the diagnosis of severe asthma,  $FE_{NO} \ge 20$  ppb is considered the cut-off characterizing Type 2 inflammation severe asthma and it is used to assess this asthma phenotype, together with other markers like blood and sputum eosinophils. It has been suggested a  $FE_{NO}$  cut point of 21 ppb best fits  $\ge 3\%$  sputum eosinophils in corticosteroid-naive patients.

Very few data from studies analyzing clinically important change of  $FE_{NO}$  in individual patients is available and different are the results depending on the considered outcome. Considering simply the within-subject coefficient of variation, in healthy subject is approximately 10% (corresponding to a raw change up to 4 ppb) while it

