#### STUDY DESIGN AND SAMPLE SIZE

This is a prospective, open-label, Phase II study. The study will consist of a single treatment phase including:

- Screening period
- 12 weeks (90 days) of treatment period.

The planned sample size for this study is 17 subjects. In order to evaluate primary and secondary outcomes, study assessments will be conducted at Day 0, 30, 60 and 90 of treatment.

The MCID for FEV1 is 12% and 200 ml measured by spirometry obtained at baseline (immediately prior to the start of the treatment) with the results obtained 2 hour after administration of study medication (2-hour postdose FEV1) after 12 weeks of treatment.

The MCID for  $FE_{NO}$  is a reduction of at least 20% in  $FE_{NO}$  for values over 50 ppb or more than 10 ppb for values lower than 50 ppb will be used as the cut point to indicate a significant response to treatment.

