# Endpoints

#### **Primary Endpoints**

- Change in mean trough FEV1 expressed as mililitres after 90 days of treatment
- Change in mean ACQ-7 scores after 90 days of treatment
- The threshold for change in ACQ-7 scores that is considered clinically important (MCID) is 0.5.

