#### **Inclusion Criteria**

All adults aged 18 years and above with a prior documented diagnosis of atopic (Th2driven) asthma by a physician based on Global initiative for Asthma (GINA) 2020 Guidelines whose asthma is uncontrolled on ICS/LABA combination therapy based on the following criteria:

- a) A well documented requirement for regular treatment with a minimum dose of either fluticasone /salmeterol combination therapy or budeosnide/formoterol combination therapy in the 12 months prior to screening with or without maintenance of oral corticosteroids (OCS).
- b) Forced expiratory volume (FEV1) > 50% to <80% predicted normal during the screening phase (3 attempts maximum) and on the randomization day prior to the first dose of IMP.
- c) Reversibility of at least 12% and 200 ml in FEV1 after 200 ug to 400 ug (2 to 4 inhalations) of salbutamol during the screening phase (3 attempts maximum), or documented history of reversibility test that met these criteria within 12 months prior to screening.

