# End of Treatment Visit (Visit 4 / Week 12/ Day 90) - CIC

Subjects will return the clinic on Day 90. Any remaining investigational product or empty packaging will be returned.

Study visit assessments will include:

- vitals signs, weight measurement
- review of concomitant therapies
- review of adverse events
- review of the diary card record
- symptoms examination
- compliance calculation
- Asthma Control Questionnaire
- Laboratory tests (basic hematology and chemistry)
- Exhaled nitric oxide (FENO) measurements, followed by
- Spirometry measurement (FEV1 and FVC)
- ECG

This visit will conclude the study.

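### The primary FEV1 change compares a baseline and a Day 90 reading whose bronchodilator state and timing are neither matched nor recorded, in a single-arm study of salbutamol-reversible patients

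*Protocol*

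**What the plan says.** **Endpoint and threshold.** Protocol, Primary Endpoints, takes the change in mean trough FEV1 "expressed as mililitres after 90 days of treatment". Objectives also says trough. Study Design and Sample Size sets the MCID at "12% and 200 ml measured by spirometry obtained at baseline", defines that baseline as just before treatment starts, and compares it "with the results obtained 2 hour after administration of study medication" at 12 weeks.

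**Population.** Inclusion Criteria requires asthma that is uncontrolled on ICS/LABA. Criterion (c) asks for "Reversibility of at least 12% and 200 ml in FEV1 after 200 ug to 400 ug (2 to 4 inhalations) of salbutamol", shown either at screening or in a documented test from the preceding 12 months. Criterion (b) asks for an FEV1 at screening and again on the randomization day before the first dose.

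**Visits.** Screening lists a spirometry measurement. The Baseline (Day 0) visit lists only a review of spirometry, and the first dose is taken the following day. The End of Treatment Visit (Day 90) lists FeNO followed by spirometry. None of these lists states whether the reading is before or after a bronchodilator, the time since the last inhaler, or the clock time.

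**FeNO.** The section Asthma and FeNO says that FeNO "could increase due to bronchodilation and it could decrease due to bronchoconstriction". On non-disease influences it adds "thus filling in a questionnaire for NO measurement is recommended". No visit list contains such a questionnaire.

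**The concern.** A single-arm before-and-after comparison attributes to the product whatever differs between the two readings. Here the patients are selected for a large FEV1 response to a short-acting bronchodilator, they use a long-acting one throughout, and the response that qualifies them equals the change the study would call clinically important. If some subjects are bronchodilated at one reading and not at the other, the difference enters the primary endpoint directly, and no control group cancels it.

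At stake is the reading of the FEV1 result. A rise could reflect an inhaler taken before the Day 90 visit. A missing rise could reflect one taken before the baseline reading, or the use of a post-salbutamol value as baseline. FeNO is affected as well: by the Protocol's own account bronchodilation can raise it, so an inhaler before the Day 90 reading could mask a fall. If inhaler times are not collected, no later analysis can separate these effects.

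**Working it through.** **1. Is a common measurement condition fixed?** The timing statements side by side:

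| Section | What it fixes |
|---|---|
| Objectives; Primary Endpoints | Trough FEV1; the term is undefined and the drug is not named |
| Study Design and Sample Size | Value just before treatment against a value 2 hours after study medication |
| Inclusion Criteria (b) | FEV1 at screening and on the randomization day, before the first dose |
| Screening | Spirometry measured |
| Baseline (Day 0) | Spirometry reviewed only |
| End of Treatment (Day 90) | Spirometry measured after FeNO |

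By the visit lists, the measured baseline is the screening reading. If reversibility is tested at screening, that visit yields a pre- and a post-salbutamol value, and the text does not say which one enters the endpoint. If criterion (c) is met from a historical test, there may be no post-salbutamol screening value.

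**2. Entry response against MCID.** Both require at least 12% and at least 200 ml, so the smallest qualifying gain is max(200 ml, 0.12 × FEV1). The two limits meet at 200 / 0.12 = 1,667 ml.
- FEV1 of 1.67 L or less: 200 ml
- FEV1 of 2.0 L: 240 ml
- FEV1 of 2.5 L: 300 ml

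At every FEV1 this is also the smallest change that meets the MCID. A flat 200 ml is the full MCID only up to about 1.67 L.

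**3. Shift in the mean, one-directional illustration.** The Protocol gives no figure for this. Assume that k subjects are bronchodilated at Day 90 but not at baseline, that each gains 200 ml, and that the product has no effect. Shift = 200 × k / N. The Protocol gives N as 17 in Study Design and Sample Size and as 10 in Study Population.

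| k | N = 17 | N = 10 |
|---|---|---|
| 3 | 600/17 = 35 ml | 60 ml |
| 5 | 1000/17 = 59 ml | 100 ml |
| 8 | 1600/17 = 94 ml | 160 ml |

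**4. Effect on a test, further assumptions.** The Protocol gives no alpha, test or SD. Assume a two-sided 5% one-sample t-test on the change, N = 17, and each subject unmatched in that direction with probability f. The simulated upper-tail rejection rate with an inert product (100,000 runs; nominal 2.5%) is:

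| f (mean shift, 200 × f) | SD 200 ml | SD 300 ml | SD 400 ml |
|---|---|---|---|
| 0% (0 ml) | 2.5% | 2.5% | 2.5% |
| 25% (50 ml) | 13.7% | 8.9% | 6.9% |
| 50% (100 ml) | 40.9% | 23.1% | 15.2% |

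With N = 10 and f = 50% the rates are 24.4%, 14.3% and 10.1%.

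**5. Mismatch in both directions.** If 8 of 17 subjects are unmatched and +200 ml and −200 ml are equally likely, the expected shift is zero. The added variance is 200² × 8/17 = 18,824 ml². An SD of 300 ml becomes √(90,000 + 18,824) ≈ 330 ml. The result is noise, not bias.

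**The case against.** The Protocol is not silent on conditions. Trough suggests a pre-dose reading, baseline is placed just before treatment, criterion (b) asks for a pre-dose FEV1, FeNO precedes spirometry, visits are fasted and concomitant therapies are reviewed. Part of this stands: baseline is not left wholly undefined, and nothing in the text says that a post-salbutamol value is meant. It does not settle the matter. Trough is undefined, conflicts with the 2-hour post-dose wording, and even as a trough of the study product would not fix inhaler timing. Day 0 only reviews spirometry. A food fast does not govern inhalers, and a review of therapies does not record the hours since the last dose.

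A reader might infer that a Day 90 reading after an inhaler will show the MCID with an inert product, or that the shifts above are a minimum bias. The documents do not support that. The qualifying response may be up to 12 months old, was used for selection, and was to 200–400 µg salbutamol. Nothing shows that it recurs in full on ICS/LABA or that the maintenance inhaler gives the same gain. Nor does the text give a reason for mismatch to run one way only.

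The FeNO questionnaire is background advice and not a commitment of this Protocol. A higher FeNO at Day 90 would also work against the product, not for it.

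Finally, a statistical analysis plan may exist. It could name the baseline value, but it cannot supply inhaler times that no visit collects.

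**Conclusion.** The point holds as a weakness in how the primary FEV1 measurement is fixed. The two readings are not matched or recorded for bronchodilator state and timing, the Protocol's timing statements conflict, and the entry criterion shows that a bronchodilator alone has produced a change of MCID size in every eligible subject at a qualifying test. Inhaler timing could therefore move the FEV1 change up or down, or blur it, with no control arm to reveal this.

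The size is unknown. About 35 to 94 ml for 3 to 8 of 17 subjects (60 to 160 ml with 10) is a one-directional scenario that rests on an assumed 200 ml gain and an assumed number of unmatched subjects. The rejection rates rest further on an assumed test, alpha and SD. The documents show that the comparison is open to this error, but not that the error will occur or that it favours the product.

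**What to change.** - Reconcile the trough, 2-hour post-dose and baseline wording across Objectives, Study Design and Sample Size, Primary Endpoints, Inclusion Criterion (b) and the Baseline visit.
- Name one pre-salbutamol reading as the baseline FEV1 and say at which visit it is measured.
- Take the baseline and Day 90 FeNO and spirometry under the same stated condition, at a similar clock time and a similar interval since the last maintenance inhaler.
- At each of these readings record clock time and time since the last short-acting and long-acting inhaler, on a short form such as the questionnaire that the FeNO section recommends. As-needed reliever use cannot be scheduled, so for that the record is what matters.
- Keep all subjects in the main analysis. Set a matching tolerance in advance and use it only for a secondary sensitivity analysis: inhaler use after baseline may itself respond to treatment, so dropping unmatched pairs could introduce selection bias in 17 (or 10) subjects.

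Any rule on withholding inhalers is for the investigators to set; this change does not need one. The cost is a one-page form, some visit scheduling and an occasional rebooked spirometry. If Day 0 is chosen as the baseline visit, one further set of measurements is needed there.

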## d) $FE_{NO}$ of > 25 ppb measured at baseline screening.

- Absence of a recent exacerbation 6 weeks prior to enrolment
- Non-smoker patient for at least six months and with a prior tobacco consumption < 10 packs/ year

- Patient with normal organ function
- Patient weight > 41 kg and body mass index (BMI) between 18 and 35 kg/m2

#### **Exclusion Criteria**

- Asthmatic patient still exposed to allergens or to triggering factors influencing asthma control
- Female subjects who are pregnant or lactating
- Chronic obstructive pulmonary disease (COPD) and/or other lung diseases imparing pulmonary function test
- Within 6 weeks prior to screening, patient who received oral corticosteroids for any other reason than to treat asthma (patients needing long term OCS to control asthma)
- Patient with history of acute infectious sinusitis or respiratory tract infection within 4 weeks prior to screening visit
- Patient presenting with cardiac disorders defined by at least one of the following conditions:

a) Patient with recent cardiac history (within 6 months) of :

- acute coronary syndrome
- acute heart failure (Class III or IV of the NYHA classification)
- significant ventricular arrhythmia (persistent ventricular tachycardia, ventricular fibrillation, resuscitated sudden death)

b) Patient with cardiac failure class III or IV of the NYHA classificationc) Patient with sever conduction disorders which are not prevented by permanent pacing (atrio-ventricular block 2 and 3, sino-atrial block)d) Syncope without known aetiology within 3 months

e) Uncontrolled severe hypertension, or symptomatic hypertension

- Patient with active lung disease other than asthma (eg. Chronic bronchitis)
- Patient who had a major surgery within 4 weeks prior to screening visit
- Patient with a life expectancy of less than 6 months
- Patient with history of primary malignancy < 5 years, except treated basal cell skin cancer or cervical carcinoma in situ.
- Patient with any severe and/or uncontrolled medical condition aside from asthma
- Patient with a known diagnosis of human immunodeficiency virus (HIV) infection
- Patient with history of poor compliance or history of drug/alcohol abuse.
- Participation in a clinical study with exposure to any non-registered drug or botanical product within 30 days prior.
- Individual has a condition the investigator believes would interfere with his or her ability to provide informed consent, comply with the study protocol, which might confound the interpretation of the study results or put the person at undue risk

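### Entry requires no period of stable allergen exposure or stable asthma therapy before Day 0, so drift from a recent change, where present, could not be told from a product effect

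*Protocol*

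**What the plan says.** **Exposure.** The Exclusion Criteria rule out an "Asthmatic patient still exposed to allergens or to triggering factors influencing asthma control". The test is of current status, and no exposure-free interval is attached.

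**Therapy.** Inclusion criterion (a) asks for "A well documented requirement for regular treatment with a minimum dose of either fluticasone /salmeterol combination therapy or budeosnide/formoterol combination therapy" and places that requirement "in the 12 months prior to screening with or without maintenance of oral corticosteroids (OCS"). The 12 months apply to the need for treatment, not to an unchanged drug or dose.

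**Look-backs that do exist.**
- Exacerbation: "Absence of a recent exacerbation 6 weeks prior to enrolment".
- Infection: "Patient with history of acute infectious sinusitis or respiratory tract infection within 4 weeks prior to screening visit".
- Oral corticosteroids: "Within 6 weeks prior to screening, patient who received oral corticosteroids for any other reason than to treat asthma". This does not reach OCS given for asthma.
- Smoking (six months), major surgery (4 weeks) and products from other trials (30 days).

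**What moves the outcome.** The Rationale (Asthma and FeNO) states "Allergen exposure is associated with higher levels of" FeNO. It adds that levels may fall in the early allergic response, and it lists anti-inflammatory drugs among the confounders.

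**Design.** The title describes an open-label, single-arm study. Every listed efficacy endpoint is a change after 90 days: FEV1 and ACQ-7 (primary); FeNO, eosinophils and IgE (secondary). There is a screening period of unstated length, and no run-in is described.

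**The concern.** The protocol names allergen exposure and anti-inflammatory drugs as influences on FeNO, and it sets time windows for several other disturbing events. It sets none for a change in these two.

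A patient whose exposure ended shortly before screening meets the wording. So does a patient whose ICS/LABA dose was raised, whose product was switched, who received an add-on, or whose maintenance OCS changed. If that change is still working through at Day 0, the outcome moves during the 90 days whether or not the product is active.

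A concurrent control would share such drift and the comparison would cancel it. Here there is only before and after, so no later analysis can recover the split. Holding therapy constant during the 90 days would not help either, because the change lies before baseline.

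FeNO has a further opening. The Baseline visit list names no FeNO measurement, so the only pre-treatment value in the visit lists is at screening. Drift between screening and Day 0 would then also enter the FeNO change.

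**Working it through.** **1. Text check.** The Inclusion Criteria, Exclusion Criteria, Screening and Baseline visit sections were read for any stability rule.

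| Source of drift | Rule at entry | Time window |
|---|---|---|
| Allergen or trigger exposure | Must not be current | None |
| ICS/LABA | Regular need over 12 months | None for an unchanged dose or drug |
| Maintenance OCS for asthma | Allowed | None |
| Exacerbation | Absent | 6 weeks |
| Respiratory infection | Absent | 4 weeks |

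**2. Plan's own figure.** The point depends on no stated figure. The sample size (17 in Study Design and Sample Size, 10 in Study Population) cannot be reproduced, because no alpha, power or SD is given. Both values are carried below.

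**3. Illustration for FeNO.** The protocol gives a within-subject coefficient of variation of about 20% in asthma. The share affected (10-30%) and their further fall (20-40%) are assumptions.
- Mean bias = share × fall: 0.10 × 20% = 2%, up to 0.30 × 40% = 12%.
- SD of a change from within-subject variation alone, with independent readings: 20% × √2 = 28.3%.
- SE: 28.3%/√17 = 6.9%; 28.3%/√10 = 8.9%.
- Bias/SE at n=17: 2/6.9 = 0.3 to 12/6.9 = 1.7.
- Bias/SE at n=10: 2/8.9 = 0.2 to 12/8.9 = 1.3.

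The SE leaves out differences between subjects in true change, so it is a lower bound and these ratios are upper bounds.

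**4. Illustration for the primary endpoints.** Assume no product effect, a share f of subjects improving by m = one MCID (200 ml, or 0.5 ACQ-7 points, both from the protocol and used only as units), and a two-sided 5% paired t-test. Bias = f × m. Total SD = √(SD² + f(1−f)m²). The chance of a false favourable result comes from the noncentral t distribution with noncentrality (bias/total SD) × √n.

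Example: FEV1, f = 25%, assumed SD 300 ml, n=17. Bias = 50 ml; total SD = √(90,000 + 7,500) = 312 ml; noncentrality = 50/312 × √17 = 0.66; chance = 9.0%.

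| n=17 | f = 0 | f = 10% | f = 25% | f = 50% |
|---|---|---|---|---|
| FEV1, SD 300 ml | 2.5% | 4.4% | 9.0% | 23% |
| FEV1, SD 200 ml | 2.5% | 5.6% | 14% | 41% |
| ACQ-7, SD 0.7 | 2.5% | 4.6% | 9.7% | 26% |
| ACQ-7, SD 1.0 | 2.5% | 3.9% | 6.9% | 15% |

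At n=10 and f = 25% the four chances are 6.6%, 9.5%, 7.0% and 5.3%. The values of f and the SDs are assumptions, as is a drift of one MCID. The protocol supplies none of them.

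**The case against.** The best case for the plan is that existing rules already limit the problem.

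- The 12-month ICS/LABA requirement makes a newly started combination unlikely. This stands. What remains is a recent dose increase, switch, add-on or OCS change.
- FEV1 must be below 80% predicted at screening and again before the first dose, so a patient who improves past that limit in between is excluded. This stands in part: a rise within the permitted band passes, drift after Day 0 is untouched, and the Baseline list mentions only a review of spirometry.
- The exacerbation and infection windows remove related drift, and the last exclusion lets the investigator reject a condition that might confound the results. These help, but set no rule for exposure or therapy.
- Concomitant therapies are already reviewed at screening and baseline. True; only an exposure record would be new.
- Any drift before baseline is a problem of single-arm designs in general. Also true, but this source can be reduced at entry.

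A reader might infer that the bias always favours the product. The documents do not support that. A recent step-down of therapy would work the other way, and the Rationale's sentence on allergen exposure also allows for lower FeNO in the early allergic response. For exposure the criterion does lean towards apparent improvement, since it admits those whose exposure has just ended and bars those whose exposure continues. A reader might also suppose that patients would end an exposure in order to qualify; nothing in the protocol bears on this.

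**Conclusion.** The gap is real: no exposure-free period and no stable-controller period is required before screening or Day 0. Where a change occurred shortly before entry, its later effect on FeNO, ACQ-7 or FEV1 could not be separated from a product effect.

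The conclusion is conditional. It would go too far to say that improvement already under way will be counted as a product effect. The protocol does not show how many subjects would have such a change, how large the drift would be, or in every case which way it would go. The FeNO and primary-endpoint figures show only that moderate assumed drift would matter at 10 or 17 subjects; they are not estimates for this trial. FeNO is listed as a secondary endpoint, although it appears in the primary objective.

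The change is worth making because it is cheap and because analysis cannot repair the loss afterwards.

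**What to change.** Keep the current exclusion for ongoing exposure. Replacing it with a rule about change alone would make patients with constant exposure eligible, and so admit a confounder that the protocol names.

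Add one criterion: known allergen or trigger exposure, and asthma controller therapy (drug and dose, including maintenance OCS), have been unchanged for a period fixed in advance before screening and through Day 0. The length is for the investigators to choose. The protocol's own 6-week exacerbation window is one available reference, but it was set for a different event.

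Record exposure history at screening, alongside the concomitant-therapy review already planned, so that the criterion can be checked.

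Cost: one eligibility line and one screening item. Some candidates would wait a few weeks or not be eligible. No change in sample size follows. Drift from this source would be largely removed; regression to the mean and open-label effects would remain.
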